4.5 STUDY ASSESSMENTS

Please see [Appendix 1](#) for the schedule of activities to be performed during the study.

4.5.1 Informed Consent Forms and Screening Log

Written informed consent for participation in the study must be obtained before any study-related procedures are performed. Informed Consent Forms for enrolled patients and for patients who are not subsequently enrolled will be maintained at the study site.

All screening evaluations must be completed and reviewed to confirm that patients meet all eligibility criteria before enrollment. The investigator will maintain a screening log to

record details of all patients screened and to confirm eligibility or record reasons for screening failure, as applicable.

4.5.2 Medical History and Demographic Data

Medical history includes clinically significant diseases, surgeries, cancer history (including prior cancer therapies and procedures), reproductive status, smoking history, and all medications (e.g., prescription drugs, vaccines, over-the-counter drugs, herbal or homeopathic remedies, and nutritional supplements) used by the patient within 7 days prior to the screening visit.

Demographic data will include age, sex, and self-reported race/ethnicity.

4.5.3 Physical Examinations

A complete physical examination should be performed at screening and should include an evaluation of the head, eyes, ears, nose, and throat, and the cardiovascular, dermatological, musculoskeletal, respiratory, gastrointestinal, and neurological systems. Any abnormality should be recorded on the General Medical History and Baseline Conditions eCRF.

At subsequent visits (or as clinically indicated), limited symptom-directed physical examinations should be performed. Changes from baseline abnormalities should be recorded in patient notes. New or worsened clinically significant abnormalities should be recorded as adverse events on the Adverse Event eCRF.

4.5.4 Vital Signs

Vital signs will include measurements of respiratory rate, heart rate, and systolic and diastolic blood pressures while the patient is in a seated position, and temperature.

Baseline vital sign assessment will be done on Cycle 1, Day 1 prior to the first dose of study drug. All subsequent vital sign assessments (i.e., during study drug cycles and treatment discontinuation visits) will be done per the local standard of care, as outlined in the schedule of activities (see [Appendix 1](#)). Specific requirements for the monitoring of vital signs during atezolizumab infusions are provided in Section [4.3.2](#).

Patients will be informed about the possibility of delayed post-infusion symptoms and instructed to contact their study physician if they develop such symptoms.

4.5.5 Tumor and Response Evaluations

Tumor assessments will be performed at screening and then every 6 weeks (± 7 days) thereafter, regardless of dose delays, for the first 12 months following Cycle 1, Day 1. After 12 months, tumor assessments will be required every 9 weeks (± 7 days) until disease progression or treatment discontinuation. Disease status (complete response [CR], partial response [PR], stable disease, or PD) will be assessed by the investigator with the use of RECIST v1.1 (see [Appendix 4](#)).

The same radiographic procedure used at screening should be used throughout the study (e.g., the same contrast protocol for CT scans). Assessments should be performed by the same evaluator, if possible, to ensure internal consistency across visits. Results must be reviewed by the investigator before dosing at the next cycle. In addition, all radiographic images will be sent to an independent review facility to standardize results and interpretation. Further details on radiographic methods are described in the IRF charter.

Bone scans (Technetium-99m) or sodium fluoride positron emission tomography (NaF-PET) may be performed at screening if clinically indicated. If bone metastases are present at screening and cannot be seen on CT or MRI scans, Technetium-99m or NaF-PET bone scans should be repeated at the discretion of the investigator when complete response is identified in the target disease or when progression in bone is suspected.

Patients who continue treatment beyond radiographic disease progression assessed per RECIST v1.1 should be monitored with a follow-up scan at the next scheduled tumor assessment when the scan frequency is every 6 weeks (± 7 days). If the scan frequency is every 9 weeks, the follow-up scan is recommended at 6 weeks (± 7 days) or earlier if clinically indicated, or per local standard of care.

For patients who discontinue study drug for any reason other than radiographic PD per RECIST v1.1, tumor assessments should continue at the same frequency as would have been followed if the patient had remained on the study drug until radiographic disease progression per RECIST v1.1 (or loss of clinical benefit for patients who continued treatment after disease progression according to RECIST v1.1), withdrawal of consent, death, or study termination by the Sponsor, whichever occurs first.

At the investigator's discretion, tumor assessments may be repeated at any time if PD is suspected.

4.5.6 Laboratory, Biomarker, and Other Biological Samples

4.5.6.1 Samples for Safety Laboratory Tests

Samples for the following safety laboratory tests will be sent to the study site's local laboratory for analysis:

- Hematology (CBC, including RBC count, hemoglobin, hematocrit, WBC count with differential [neutrophils, eosinophils, lymphocytes, monocytes, basophils, and other cells], and platelet count)
- Serum chemistries (glucose, BUN or urea, creatinine, sodium, potassium, magnesium, chloride, bicarbonate or total CO₂, calcium, phosphorus, total and direct bilirubin, ALT, AST, alkaline phosphatase, LDH, total protein, and albumin)
- Coagulation (aPTT or INR)
- For all women of childbearing potential (including those who have had a tubal ligation), a serum pregnancy test at screening. Urine pregnancy tests will be

performed at specified subsequent visits (see [Appendix 1](#)). If a urine pregnancy test is positive, it must be confirmed by a serum pregnancy test.

- Urinalysis (specific gravity, pH, glucose, protein, ketones, and blood); dipstick permitted
- Thyroid function testing (thyroid-stimulating hormone, free T3, free T4)
- HBV serology: HBsAg, total HBcAb
 - If a patient has a negative HbsAg test and a positive total HBcAb test at screening, an HBV DNA test should be performed at screening.
- HCV serology: HCV antibody and (if HCV antibody test is positive) HCV RNA
 - If a patient has a positive HCV antibody test at screening, an HCV RNA test must be performed to determine if the patient has an active HCV infection.
- HIV testing
 - All patients will be tested for HIV prior to inclusion in the study; HIV-positive patients will be excluded.
- EGFR testing
 - If EGFR testing is not available as a part of standard-of-care diagnostic workup, contact the Medical Monitor for additional options. (See [Section 4.1.2](#) for exclusion criteria).

4.5.6.2 Biomarker Samples

A central laboratory will coordinate the sample collection of tissue and blood samples for research-related testing at central laboratories or at the Sponsor. Instruction manuals and supply kits will be provided for all central laboratory assessments. Samples for the following laboratory tests will be sent to one or several central laboratories or to the Sponsor for analysis:

- Biomarker assays in blood samples
 - Blood samples will be obtained for biomarker evaluation (including but not limited to biomarkers related to NSCLC or tumor immune biology) from all eligible patients according to the schedule in [Appendix 2](#). Samples will be processed to obtain plasma and PBMCs for the determination of changes in blood-based biomarkers (e.g., ctDNA). Whole-blood samples may be processed to obtain their derivatives (e.g., RNA and DNA) and evaluated for immune-related, tumor type-related, and other exploratory biomarkers (e.g., alterations in gene expression or single-nucleotide polymorphisms).
 - Any remaining samples collected for biomarker assays may be used for exploratory biomarker profiling, identification, and pharmacodynamic assay development purposes as appropriate.
- Optional collection of tumor tissue
 - Although this study includes all otherwise-eligible patients irrespective of tissue-related biomarker status, tissue biopsies (tissue blocks preferred) may be submitted at any time during the study, with biopsies from diagnosis (archival or

fresh) and at progression preferred, for exploratory biomarker and correlative analysis. If tissue samples are submitted, NGS may be performed by Foundation Medicine. If performed by Foundation Medicine, the investigator can obtain results from these analyses in the form of an NGS report, which is available upon request directly from Foundation Medicine. The investigator may share and discuss the results with the patient, unless the patient chooses otherwise. The Foundation Medicine NGS assay, FoundationOne[®], has not been cleared or approved by health authorities. The NGS report is generated for research purposes and is not provided for the purpose of guiding future treatment decisions (see Section 4.5.7). Results may not be available for samples that do not meet testing criteria

- Representative formalin-fixed paraffin-embedded tumor specimens in paraffin blocks (blocks preferred) from a recent (the most recent diagnosis of metastatic NSCLC) biopsy specimen with a minimum volume of 0.2mm³ viable tumor tissue can be provided at any time during the study. Tissue quality should be confirmed by a local pathologist and should adhere to the Foundation Medicine Pathology Review Process for Optimal Tissue Utilization.
- Fine-needle aspiration, brushing, cell pellet from pleural effusion, bone metastases, and lavage samples are not acceptable. For core-needle biopsy specimens, at least 3 cores should be submitted for evaluation.
- Patients who do not have tissue specimens meeting eligibility requirements may still be eligible for enrollment provided all other eligibility criteria are met. Acceptable samples include core needle biopsies for deep tumor tissue (minimum 3 cores) or excisional, incisional, punch, or forceps biopsies for cutaneous, subcutaneous, or mucosal lesions.

For patients who consent to the optional collection of samples for the Research Biosample Repository (RBR), any leftover material from the above sample collection will be stored and used for exploratory analyses as indicated in Section 4.5.7.

Exploratory biomarker research may include, but will not be limited to, the biomarkers listed in [Appendix 2](#).

For sampling procedures, storage conditions, and shipment instructions, see the laboratory manual.

Unless the patient gives specific consent for his or her leftover samples to be stored for optional exploratory research (see Section 4.5.7), biological samples will be destroyed when the final Clinical Study Report has been completed, with the following exception(s):

- PBMCs and plasma and tumor tissue samples collected for biomarker analysis will be destroyed no later than 15 years after the final Clinical Study Report has been completed.

When a patient withdraws from the study, samples collected prior to the date of withdrawal may still be analyzed, unless the patient specifically requests that the samples be destroyed or local laws require destruction of the samples.

Data arising from sample analysis, including data on germline mutations, will be subject to the confidentiality standards described in Section [4.5.7.4](#).

4.5.7 Optional Samples for Research Biosample Repository

4.5.7.1 Overview of the Research Biosample Repository

The RBR is a centrally administered group of facilities used for the long-term storage of human biological specimens, including body fluids, solid tissues, and derivatives thereof (e.g., DNA, RNA, proteins, and peptides). The collection, storage, and analysis of RBR specimens will facilitate the rational design of new pharmaceutical agents and the development of diagnostic tests, which may allow for individualized drug therapy for patients in the future.

Specimens for the RBR will be collected from patients who give specific consent to participate in this optional research. RBR specimens will be used to achieve the following objectives:

- To study the association of biomarkers with efficacy, adverse events, or disease progression
- To increase the knowledge and understanding of disease biology
- To study drug response, including drug effects and the processes of drug absorption and disposition
- To develop biomarker or diagnostic assays and establish the performance characteristics of these assays

4.5.7.2 Approval by the Institutional Review Board or Ethics Committee

Collection and submission of biological samples to the RBR is contingent upon the review and approval of the exploratory research and the RBR portion of the Informed Consent Form by each site's Institutional Review Board (IRB) or Ethics Committee (EC) and, if applicable, an appropriate regulatory body. If a site has not been granted approval for RBR sampling, this section of the protocol (Section [4.5.7](#)) will not be applicable at that site.

4.5.7.3 Sample Collection

The following samples will be stored in the RBR and used for research purposes, including, but not limited to, research on biomarkers related to atezolizumab or diseases:

- Blood samples and/or plasma and/or PMBCs collected at screening; on Day 1 of Cycles 1, 2, 3 and 4; and at first evidence of radiographic progression or loss of clinical benefit

- Tumor (e.g., primary tumor, metastatic site, or site of local recurrence or advancement, if appropriate) samples collected at diagnosis or later
- Leftover blood, serum, plasma, PBMC, and tumor tissue samples

The above samples may be sent to one or more laboratories for DNA extraction to enable analysis of germline mutations or somatic mutations via whole genome sequencing (WGS), whole exome sequencing (WES), NGS, or other genomic analysis methods.

Genomics is increasingly informing researchers' understanding of disease pathobiology. WGS and WES provide a comprehensive characterization of the genome and exome, respectively, along with clinical data collected in this study, may increase the opportunity for developing new therapeutic approaches. Data will be analyzed in the context of this study, but will also be explored in aggregate with data from other studies. The availability of a larger dataset will assist in the identification of important pathways, guiding the development of new targeted agents.

For sampling procedures, storage conditions, and shipment instructions, see the laboratory manual.

RBR specimens are to be stored until they are no longer needed or until they are exhausted. However, the RBR storage period will be in accordance with the IRB/EC-approved Informed Consent Form and applicable laws (e.g., health authority requirements).

4.5.7.4 Confidentiality

Specimens and associated data will be labeled with a unique patient identification number.

Patient medical information associated with RBR specimens is confidential and may be disclosed to third parties only as permitted by the Informed Consent Form (or separate authorization for use and disclosure of personal health information) signed by the patient, unless permitted or required by law.

Given the complexity and exploratory nature of the analyses, data derived from RBR specimens will generally not be provided to study investigators or patients unless required by law. The aggregate results of any conducted research will be available in accordance with the effective Sponsor policy on study data publication.

Data generated from RBR specimens must be available for inspection upon request by representatives of national and local health authorities and Sponsor monitors, representatives, and collaborators, as appropriate.

Any inventions and resulting patents, improvements, and/or know-how originating from the use of the RBR data will become and remain the exclusive and unburdened property of the Sponsor, except where agreed otherwise.

4.5.7.5 Consent to Participate in the Research Biosample Repository

The Informed Consent Form will contain a separate section that addresses participation in the RBR. The investigator or authorized designee will explain to each patient the objectives, methods, and potential hazards of participation in the RBR. Patients will be told that they are free to refuse to participate and may withdraw their specimens at any time and for any reason during the storage period. A separate, specific signature will be required to document a patient's agreement to provide optional RBR specimens. Patients who decline to participate will not provide a separate signature.

The investigator should document whether or not the patient has given consent to participate and (if applicable) the date(s) of consent, by completing the RBR Research Sample Informed Consent eCRF.

In the event of an RBR participant's death or loss of competence, the participant's specimens and data will continue to be used as part of the RBR research.

A separate, specific signature is not required for the following mandatory RBR samples:

- Blood taken at screening, baseline, and progression

4.5.7.6 Withdrawal from the Research Biosample Repository

Patients who give consent to provide RBR specimens have the right to withdraw their specimens from the RBR at any time for any reason. If a patient wishes to withdraw consent to the testing of his or her specimens, the investigator must inform the Medical Monitor in writing of the patient's wishes through use of the appropriate RBR Subject Withdrawal Form and, if the study is ongoing, must enter the date of withdrawal on the RBR Research Sample Withdrawal of Informed Consent eCRF. The patient will be provided with instructions on how to withdraw consent after the study is closed. A patient's withdrawal from Study ML39237 does not, by itself, constitute withdrawal of specimens from the RBR. Likewise, a patient's withdrawal from the RBR does not constitute withdrawal from Study ML39237.

4.5.7.7 Monitoring and Oversight

RBR specimens will be tracked in a manner consistent with Good Clinical Practice by a quality-controlled, auditable, and appropriately validated laboratory information management system to ensure compliance with data confidentiality, as well as adherence to authorized use of specimens as specified in this protocol and in the Informed Consent Form. Sponsor monitors and auditors will have direct access to appropriate parts of records relating to patient participation in the RBR for the purposes of verifying the data provided to the Sponsor. The site will permit monitoring, audits,

IRB/EC review, and health authority inspections by providing direct access to source data and documents related to the RBR samples.

4.5.8 On-Study Survival Follow-Up

While in the study, patients will be followed for survival and anti-cancer therapy. Survival follow-up assessments will occur at specified intervals until study completion or discontinuation. Assessments will include survival status, date of death, cause of death, and any new anti-cancer treatment.

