4.6 PATIENT, TREATMENT, STUDY, AND SITE DISCONTINUATION

4.6.1 Patient Discontinuation

Patients have the right to voluntarily withdraw from the study at any time for any reason. In addition, the investigator has the right to withdraw a patient from the study at any time. Reasons for withdrawal from the study may include, but are not limited to, the following:

- Patient withdrawal of consent at any time
- Any medical condition that the investigator or Sponsor determines may jeopardize the patient's safety if he or she continues in the study
- Investigator or Sponsor determines that it is in the best interest of the patient
- Patient non-compliance
- Patient is lost to follow-up

Every effort should be made to obtain information on patients who withdraw from the study. The primary reason for withdrawal from the study should be documented on the appropriate eCRF. However, patients will not be followed for any reason after consent has been withdrawn. Patients who withdraw from the study will not be replaced.

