4.6.2 Study Treatment Discontinuation

Patients must discontinue study drug if they experience any of the following (but will remain in the study and be evaluated for safety and efficacy):

- Pregnancy
- Intolerable toxicity related to study drug
- Any medical condition that may jeopardize the patient's safety if he or she continues with study drug
- Use of another systemic anti-cancer therapy (see Section 4.1.2)
- Radiographic disease progression per RECIST v1.1
 - **Exception:** Patients will be permitted to continue atezolizumab after RECIST v1.1 criteria for PD are met if they meet all of the following criteria:
 - Evidence of clinical benefit (defined as the stabilization or improvement of disease-related symptoms) as assessed by the investigator
 - Absence of symptoms and signs (including worsening of laboratory values [e.g., new or worsening hypercalcemia]) indicating unequivocal progression of disease
 - No decline in ECOG Performance Status that can be attributed to disease progression
 - Absence of tumor progression at critical anatomical sites (e.g., leptomeningeal disease) that cannot be readily managed and stabilized by protocol-allowed medical interventions prior to repeat dosing

When a patient discontinues study drug, regardless of the reason for discontinuation, the patient will be asked to return to the clinic within 30 days after the last dose of study drug for a study drug discontinuation visit. The visit at which the decision is made to discontinue treatment (e.g., loss of clinical benefit is confirmed or disease progression occurs) may be used as the study-drug discontinuation visit. The primary reason for study drug discontinuation should be documented on the appropriate eCRF. Patients who discontinue study drug prematurely will not be replaced.

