Appendix 1a Schedule of Activities

Activity	Screening ^a	All Treatment Cycles ^b		Treatment DC ^c	On-Study Follow-Up	Study Completion/ DC ^d	Optional Long-Term Follow-Up ^e
	Days -28 to -1	Day 1, Cycle 1	Day 1, Cycle 2 and Beyond Every 21 (\pm 3) Days	\leq 30 Days after Last Dose of Study Treatment	Every 3 Months until Study Completion/DC	\leq 30 Days after Study Completion/DC	
Urinalysis ^p	x						
HIV, HBV, HCV serology ^q	x						
EGFR/ALK testing	x ^r						
Whole-blood samples for biomarker analyses ^s (mandatory)	x	Day 1 of Cycles 2 and 4, and at disease progression or loss of clinical benefit					
Whole-blood sample for RBR ^s & exploratory biomarker analyses (optional) ^{s, t}			Day 1, Cycle 3 only				
Tissue biopsies ^s (optional)	x ^u	x ^u		x ^u			
Study drug administration ^v		x	x				
Tumor response assessment ^w	x ^w	Every 6 weeks (\pm 7 days) during treatment regardless of dose delays, for the first 12 months following Cycle 1, Day 1. After 12 months, tumor assessment will be required every 9 weeks (\pm 7 days). ^w					
Adverse events ^x	x	x	x	x	x	x	
Survival and anti-cancer therapy follow-up ^y					x		
Long-term survival follow-up (optional) ^e							x

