- ^d A patient is considered to have completed the study if he or she does not discontinue from the study prior to the end of the study. The end of this study is defined as the date after which all enrolled patients who remain alive have been followed for at least 18 months from the start of study drug. Thereafter, patients will be followed for long-term survival. Patients who complete the study will return to the clinic for a study completion visit within 30 days following study completion. Patients who discontinue the study prematurely will return to the clinic for a study discontinuation visit within 30 days following discontinuation from the study.
- ^e For patients who provide consent for optional long-term follow-up, refer to *Appendix 1b* for the schedule of assessments.
- ^f Informed consent must be documented before any study-specific screening procedure is performed, and may be obtained no more than 28 days before initiation of study drug.
- ^g Includes clinically significant diseases, surgeries, cancer history (including stage and date of diagnosis, prior cancer therapies, and procedures), reproductive status, and smoking history.
- ^h Includes heart rate, respiratory rate, and systolic and diastolic blood pressures while the patient is in a seated position, and temperature. For specific requirements during atezolizumab infusions, refer to Section 4.3.2.

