- ^x All serious adverse events and adverse events of special interest, regardless of relationship to study drug, will be reported until 90 days after the last dose of study drug or initiation of new anti-cancer therapy, whichever occurs first. All other adverse events, regardless of relationship to study drug, will be reported until 30 days after the last dose of study drug or initiation of new anti-cancer therapy, whichever occurs first. After this period, the investigator should report any serious adverse events or adverse events of special interest.
- ^y Survival follow-up should continue until at least 18 months following the start of the study for each patient and at end of study defined as 18 months after the last patient's C1D1, death, withdrawal of consent, the patient is lost to follow-up, or whichever occurs first.

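### Protocol Section 4.5.8 and Appendix 1a footnote y disagree on whether survival follow-up ends when the investigator or Sponsor withdraws a patient who has not withdrawn consent, so some deaths may go uncollected and OS may be biased slightly upward

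*Protocol*

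**What the plan says.** Four places in the protocol govern how long survival is followed during the study.

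- Section 4.5.8: "Survival follow-up assessments will occur at specified intervals until study completion or discontinuation".
- Appendix 1a, on-study follow-up column: "Every 3 Months until Study Completion/DC". Footnote d shows that discontinuation can be one patient's and not only the whole study's: "Patients who discontinue the study prematurely will return to the clinic for a study discontinuation visit within 30 days following discontinuation from the study".
- Appendix 1a, footnote y: follow-up runs to at least 18 months and the end of study, or to "death, withdrawal of consent, the patient is lost to follow-up, or whichever occurs first". Withdrawal by the investigator is not in this list.
- Section 4.6.1: "In addition, the investigator has the right to withdraw a patient from the study at any time". The listed reasons include a medical condition that may endanger the patient, non-compliance, and "Investigator or Sponsor determines that it is in the best interest of the patient". The section adds: "Every effort should be made to obtain information on patients who withdraw from the study". It bars further follow-up only once consent has been withdrawn.

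Section 4.6.2 deals with stopping study drug. Those patients stop treatment "but will remain in the study and be evaluated for safety and efficacy".

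For analysis, protocol 6.4.2 and SAP 4.5.2 count deaths from any cause that occur during the study. Patients not known to have died are censored at the last study assessment or the last date known alive.

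**The concern.** The two stopping rules give different data for the same patient. Take someone whom the investigator withdraws from the study because of a medical condition, who has not withdrawn consent and can still be reached. Under footnote y the 3-monthly contact goes on and the death is recorded. Under 4.5.8 and the column header the contact ends and the patient is censored as alive.

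Kaplan-Meier estimation treats a censored patient as having the same future risk as those still followed. That is doubtful when the reason for leaving was failing health or a judgement about the patient's best interest. Deaths then drop out of the numerator and estimated OS is too high. In a single-arm study no control arm shares the error. Sections 4.6.1 and 4.6.2 also list nearly the same medical-condition reason, one for leaving the study and one for stopping drug, so two sites could classify the same patient differently. Neither document plans a sensitivity analysis for informative censoring.

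**Working it through.** **Who is affected.** Compare the two rules by reason for leaving:

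| Reason | 4.5.8 and column header | Footnote y |
|---|---|---|
| Death, or end of study | stops | stops |
| Consent withdrawn | stops | stops |
| Lost to follow-up | stops | stops |
| Study drug stopped only (4.6.2) | continues | continues |
| Withdrawn by investigator or Sponsor, consent intact | stops | continues |

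Only the last row differs.

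**The plan's own dropout figure.** Neither document states a figure for this effect. The only dropout rate is the 5% behind the SAP 4.1 power table. That table reproduces with the Schoenfeld formula, power = Φ(|ln HR|·√(D·f·(1−f)) − 1.645), where D is the number of events and f the share of patients in one group. I used exponential PFS with a 4-month median in the shorter group, 12 months of accrual, 18 months of further follow-up, and 5% read as a yearly rate. For HR 0.6 and f = 0.5, D = 138.2, so 0.511 × √(138.2 × 0.25) − 1.645 = 1.36 and power is 91.3% (SAP: 92%). At the 25th and 75th percentile cuts the results are 82.4% and 83.7% (SAP: 83% and 84%). This calculation treats the 5% as unrelated to outcome, so it makes no allowance for the problem here.

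**Size of the OS bias.** Inputs: a median OS of 12.5 months (protocol 3.3.2, for first-line therapy) as an illustration, and a share p of would-be deaths preceded by such a withdrawal and never collected. The documents do not give p. I take 1% to 5%. The upper end equals the SAP's total dropout, which would already include consent withdrawal and loss to follow-up.

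With exponential survival, losing a share p of deaths just before they occur multiplies the observed hazard by (1−p):

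- apparent median = 12.5/(1−p)
- apparent 18-month OS = 0.5^((1−p) × 18/12.5)

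| p | Median OS (months) | 18-month OS |
|---|---|---|
| 0 | 12.5 | 36.9% |
| 1% | 12.5/0.99 = 12.6 | 37.2% |
| 2% | 12.5/0.98 = 12.8 | 37.6% |
| 5% | 12.5/0.95 = 13.2 | 38.7% |

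The formula is an upper case, because it places the withdrawal immediately before death. A simulation of 400,000 patients, with censoring at 18 to 30 months and withdrawal 1 or 3 months before death, gave medians of 13.1 and 13.0 months at 5%, and 18-month OS of 38.6% and 38.4%.

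**Hazard ratio by bTMB group.** If p is the same in both groups, the apparent HR is HR × (1−p)/(1−p) = HR. A true 0.60 stays at 0.60. It moves only if p differs between groups.

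**ORR.** Protocol 6.4.1 counts every treated patient without a confirmed response as a non-responder, so lost follow-up cannot raise it.

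**Scans and PFS.** Section 4.5.8 does not govern scans. Section 3.1 and footnote w list study discontinuation as a stop, but both then say that scans go on in the absence of progression unless consent is withdrawn. Section 4.5.5, for patients off drug without radiographic progression, stops scans at progression or loss of clinical benefit, consent withdrawal, death or termination by the Sponsor. The lists do not match, and this is a separate inconsistency from the survival one.

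**The case against.** The best defence is that the protocol, read as a whole, means to keep following these patients. Section 4.6.2 keeps anyone who stops drug for a medical condition in the study, so a deteriorating patient should by default remain under follow-up. Section 4.6.1 forbids follow-up only after consent withdrawal, which implies that other withdrawn patients may be followed and fits footnote y. Optional long-term follow-up, with an OS update (protocol 4.5.9 and 6), could recover some deaths.

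Much of this stands, and it is why the affected group is probably small. It does not remove the conflict. Section 4.5.8 and the column header still end contact, the general request for information names neither vital status nor a schedule, and long-term follow-up needs extra consent and starts only after the study ends or is terminated.

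A reader might infer three stronger things that the documents do not support:

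- That PFS is overstated by the same route. PFS depends on the scan rules, which conflict with each other but twice say that scans continue unless consent is withdrawn. Study discontinuation in Section 3.1 may also mean termination of the whole study, since consent withdrawal is listed beside it.
- That the bTMB comparison is biased. This needs withdrawal to differ by bTMB group. Blood samples are tested retrospectively (notes to the study schema), so knowledge of bTMB cannot drive the decision.
- That 10% or more of events are lost. This would be double the SAP's total dropout, and nothing in the documents supports it.

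**Conclusion.** The contradiction is real and sits within the protocol, including within Appendix 1a itself. It concerns only patients withdrawn by the investigator or Sponsor with consent intact. For them, deaths may go uncollected and OS may be censored informatively, in the direction of an overstated curve.

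At an assumed 1% to 5% of would-be deaths affected, a 12.5-month median would read about 12.6 to 13.2 months, and 18-month OS would rise from 36.9% to between 37.2% and 38.7%. These figures rest on exponential survival, on withdrawal shortly before death, and on a rate that the documents do not give. Withdrawals unrelated to prognosis, as some for non-compliance may be, would not produce this bias. The HR is unchanged if withdrawal is equal across bTMB groups, and ORR is not affected.

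The point is worth correcting because the remedy is cheap and deaths not collected may not be recoverable at analysis. It does not show that the study's OS or PFS results are materially wrong.

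**What to change.** - In Section 4.5.8 and the Appendix 1a follow-up column, replace the present stop with footnote y's events: 18 months/end of study, death, withdrawal of consent, loss to follow-up.
- In Section 4.6.1, state that withdrawal from the study for any reason other than consent withdrawal or loss to follow-up does not end vital-status contact.
- Separately, reconcile the scan-stopping lists in Section 3.1, Section 4.5.5 and footnote w, because they determine when PFS is censored.

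These changes concern data collection only. The rules for stopping treatment should stay as they are. The cost is protocol wording and a few additional 3-monthly contacts for the patients concerned.
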